Design Considerations. Mobile phones—access and confidentiality. Participants will need their own phones to enroll in the study. Participants are advised to password-protect their phones if possible yet many do not have this option. We will therefore (a) never send messages with identifying information or directly refer to HIV or HIV treatment, and (b) only enroll YPLH who agree to the risk of game messages being seen by others who use their phone. Phone numbers and de-identified patient information is securely stored in a HIPAA- compliant cloud database hosted by Dimagi. Only select study staff will be able to link participant names with ID numbers. Information will be stored and destroyed following HIPAA and IRB procedures (see Protection of Human Subjects). Assessments: Assessments will take 1 hour to complete and be administered in a private room in the Clinic using ACASI at baseline and 6- and 12-months post-baseline. Clinic records will also be coded for biologic outcomes and clinic visits at these

assessments. Participants will be remunerated 40 Cedis (\$8) for each one. They will also be given 80 Cedis worth of prepaid phone credits to send and receive text messages at the baseline and first follow-up assessments.

Measures: The measures below will evaluate HIV-related health functioning, knowledge, attitudes, and behavior. Measures previously used in Ghanaian or SSA

adolescent or young adult samples were chosen when possible. If necessary, revisions to measures will be made based on formative work to ensure cultural relevancy. **Primary**

Outcomes: Past 30-day adherence will be assessed using a 3-item measure recently developed via intensive cognitive interviewing and field tests (47) and validated against electronic drug monitoring(48) . Self report of four day ART adherence based on percent of doses taken will also be assessed using the AACTG questionnaire (49). Staff will abstract from the clinic record number of medical visits kept and missed in the past 6 months(50), and most recent HIV viral load measurement, CD4 count, and current ART schedule. See Appendix 2 for data extraction form. If viral load was not measured in the past 3 months, it will be assessed at this visit as part of routine clinical care. **Secondary**

[figure not shown]
Outcomes: Figure 5 presents an assessment schedule for each aim and describes the secondary outcomes. Appendix 3 contains questionnaire.

Data Analytic Plan

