All participants will be assigned a unique participant identification number (PIN). These PINs will be used to identify participants on research materials, surveys, transcripts, ACASI logs, tracking forms and all databases. Participants' names or other individually identifying information will never appear in any report resulting from this project. Separate from research records, an identifier key will be created to link the PIN to participant names and contact information in order to facilitate follow-up with participants and enter in data collected through record review (i.e., biologic functioning and clinic attendance). This identifier key will be stored separately from any research data or research-related forms (e.g. informed consent forms). All research data, research-related forms, and the identifier key will be secured in a locked cabinet or a password protected, encrypted laptop in a locked room. Electronic data will be routinely backed up onto an encrypted external hard drive. Encrypted data will be transferred via encrypted files to the co-PI ([name]) for quality control. Only essential project staff will have access to project data. To track participants, PI, co-PIs, and Project Coordinator will have access to a password-protected master file list linking PINs to patient records, kept in an encrypted laptop under lock and key. Electronic data will have several protections: (1) data will be securely transferred with an encrypted cloud-hosted platform (OneDrive) from Ghana to Rhode Island Hospital's data-encrypted

servers; (2) all study staff will be trained in participant data confidentiality protocols and will be consistently monitored by the co-PI on data safety and confidentiality; (3) audio files generated from the qualitative interviews will be designated with a code to ensure name confidentiality and delivered securely to a HIPAA-compliant transcription service.

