1. Potential Coercion. The risk of potential coercion to participate will be minimized by following standard procedures for obtaining the informed consent from participants. Study personnel will fully explain the study procedures, risks, benefits, and alternatives to participants. Participants will also be reminded that study participation is voluntary and that refusing to participate or withdrawing from the study at any time will not result in any negative consequences. Recruitment for both phases of the project (Development Phase and Randomized Pilot Phase) will involve the same screening procedures.

2. Emotional discomfort. Discussing sensitive topics such as HIV infection and sexual behaviour may cause psychological distress. Study staff will continually monitor the participant for signs of distress during interviews, assessments, and introductions to the text message intervention. If signs of distress are apparent, the interviewer will offer to pause the session until the participant feels well enough to carry on and also offer more counselling and support. The participant will also be reminded that they may stop the session or un-enrol from the study at any time without penalty. In addition, the Co-PI is a US-based licensed clinical psychologist, who, while working through the PI and Project Coordinator (if not on site himself), will offer clinical advice for participants experiencing emotional distress or in need of psychological and/or psychiatric care. Participants in need of psychological or psychiatric help will be given a referral to these services.

3. Breach of confidentiality. During the consent process, risks of breaches in confidentiality will be highlighted including legal norms that would require a break in confidentiality. Research staff will receive training on the importance of keeping participant information confidential through proper record-keeping. No participant information including name, phone number, and health records will be shared with other participants in the open trial and randomized pilot through the Text-Based Adherence Game. No text messages received as part of this intervention will include this information either. Participants in the youth advisory group will also be informed

during the consent process that, while the rules of participating in the group include keeping other group member's participation in the group private, this cannot be guaranteed.

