Appendix 3: Questionnaire and Satisfaction Surveys

ALL QUESTIONNAIRE ITEMS WILL BE READ TO PARTICIPANTS AND ADMINISTERED BY A COMPUTER PROGRAM WITH RESEARCH STAFF PRESENT FOR ASSISTANCE.

Demographic Survey

Age	
Gender	1- Male 2- Female 3- Other
Ethnicity	1- Akan 2- Ga/Dangbe 3- Ewe 4- Northern Tribes 5- Multiple 6- Other
What language do you speak at home?	1- Twi/Fante/Bono 2- Ga/Dangbe 3- Hausa 4- Ewe 5- English 6- Other
Location of home	1- Kumasi 2- Outside of Kumasi
Distance traveled to Fevers Unit	1- 5km or less 2- 6-10km 3- 11-15km 4- 16-20km 5- 21-25km 6- 26-30km 7- 31-35km 8- 36-40km 9- 41km or more
Time to travel to Chest Clinic	1- less than 30 minutes 2- 30 minutes to 1 hour 3- 1-2 hours 4- more than 2 hours
How do you get to Chest clinic?	1- Public transportation 2- Walk 3- Private car 4- Other
How much does it cost you (GHS) to get to Chest clinic?	
Highest Education Completed	1- None 2- Primary 3- Secondary 4- Higher education

Currently in school	1- Yes, secondary (boarding school) 2- Yes, secondary (not boarding school) 3- Yes, higher education 4- No
Live with parents or caregivers	1- Yes 2- No
Parents died as a result of AIDS	1 - Yes, one parent 2 - Yes, two parents 3 - No
Does anyone else you live with have HIV?	1- Yes 2- No
Sexual orientation	1- Straight (heterosexual) 2- Gay or lesbian (homosexual) 3- Bisexual 4- Other
Marital status	1- Single/never married 2- Married 3- Divorced/separated 4- Widowed
Relationship status	1- In a relationship, living with partner 2- In a relationship, not living with partner 3- Not in a relationship
HIV status of partner	1- HIV positive 2- HIV negative 3- Not sure
Do you have children?	1- Yes 2- No
If yes, how many?	
Religion	1- No religion 2- Catholic/Anglican 3- Protestant 4- Other Christian 5- Muslim 6- Traditionalist/spiritualist 7- Other
Employment	1- Unemployed 2- Self-employed 3- Private or government employment
Monthly household income (GHS)	1- No income 2- 1-99 GHS per month 3- 100-199 GHS per month 4- 200-299 GHS per month 5- 300-399 GHS per month 6- 400-499 GHS per month 7- 500 GHS or more per month

How many people are in your household?	_____
Which of the following best describes the main dwelling where you live?	1. Formal dwelling (such as a house) 2. Informal dwelling (such as shack or tent)

Subjective Social Standing

Instructions – First Ladder

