Below is a list of problems people sometimes have. For each please indicate how much that problem has distressed or bothered you during the past 14 days including today. How much have you been distressed or bothered during the past 14 days, (including today) by:

	NOT AT ALL	A LITTLE BIT	MODERATELY	QUITE A BIT	EXTREMELY
1. Faintness or dizziness	0	1	2	3	4
2. Feeling no interest in things	0	1	2	3	4
3. Nervousness or shakiness inside	0	1	2	3	4
4. Pains in heart or chest	0	1	2	3	4
5. Feeling lonely	0	1	2	3	4
6. Feeling tense or keyed up	0	1	2	3	4
7. Nausea or upset stomach	0	1	2	3	4
8. Feeling blue	0	1	2	3	4
9. Suddenly scared for no reason	0	1	2	3	4
10. Trouble getting your breath	0	1	2	3	4
11. Feelings of worthlessness	0	1	2	3	4
12. Spells of terror or panic	0	1	2	3	4
13. Numbness or tingling in parts of your body	0	1	2	3	4
14. Feeling hopeless about the future	0	1	2	3	4
15. Feeling so restless you couldn't sit still	0	1	2	3	4
16. Feeling weak in parts of your body	0	1	2	3	4
17. Thoughts of ending your life	0	1	2	3	4
18. Feeling fearful	0	1	2	3	4

Perceived Neighborhood Quality

The following is measure of perceived neighborhood quality originally developed in the U.S.

Instructions: Please answer the following questions about your neighborhood.

True – 1 False - 2

- 01: When there is a problem around here the neighbours get together to deal with it
- 02: This is a close-knit neighbourhood
- 03: When you get right down to it no one in your neighbourhood cares much about what happens to you
- 04: There are adults in your neighbourhood that children can look up to
- 05: People around here are willing to help their neighbours
- 06: People in this neighbourhood generally don't get along with each other
- 07: You can count on adults in your neighbourhood to watch out that children are safe and don't get into trouble
- 08: If you had to borrow 40 cedi in an emergency you could borrow it from a neighbor.
- 09: When you are away from home you know that your neighbours will keep their eyes open for possible trouble at your place
- 10: In the neighbourhood people mostly go their own way
- 11: People in your neighbourhood share the same values
- 12: If you were sick you could count on your neighbours to go to the market for you
- 13: People in your neighbourhood can be trusted
- 14: Parents in your neighbourhood know their children's friends
- 15: Children in your neighbourhood have nowhere to play but the street

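### In the visible text, support starts from observed distress or recognised need, so a calm participant who endorses the suicidal-thoughts item could leave the visit without that answer being seen

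*Combined protocol and SAP*

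**What the plan says.** The Mental Health Symptoms scale in Appendix 3 has 18 items scored 0 to 4. Each asks how much a problem has bothered the participant in the past 14 days, with today included. Item 17 reads "Thoughts of ending your life". No other item in the printed questionnaire, including the depression scale, asks this directly. No scoring rule, threshold or alert is printed beside it.

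On mode, the Design Considerations section says: "Assessments will take 1 hour to complete and be administered in a private room in the Clinic using ACASI". Appendix 3 adds that items are "ADMINISTERED BY A COMPUTER PROGRAM WITH RESEARCH STAFF PRESENT FOR ASSISTANCE".

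The response to distress is under Protection Against Risk, item 2 (Emotional discomfort):

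- Monitoring: "Study staff will continually monitor the participant for signs of distress during interviews, assessments, and introductions to the text message intervention".
- Trigger: "If signs of distress are apparent, the interviewer will offer to pause the session". The offer of further counselling stands in the same sentence, under the same condition.
- Advice: the Co-PI, a licensed clinical psychologist, "will offer clinical advice for participants experiencing emotional distress or in need of psychological and/or psychiatric care".
- Referral: "Participants in need of psychological or psychiatric help will be given a referral to these services".

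**The concern.** The Potential Risks section names emotional discomfort from talking about sensitive subjects, and the safeguard is built for that: distress that the session provokes and that staff can see. Item 17 picks up something different. Suicidal thinking may precede the visit and need not show, and when the answer goes into a computer, staff need not hear or see it.

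Because the item covers today, the useful time to act is while the participant is still in the clinic. If the only working triggers are what staff notice and what the participant says aloud, the study asks a direct question about suicidal thoughts and may not learn the reply until the data are read later. The stake is participant safety; the analysis is not touched.

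**Working it through.** The check is textual: does any visible sentence link an item 17 answer to an action at the same visit?

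1. **Item and mode.** Item 17 is self-entered by audio-assisted computer interview. Staff are present to help, which is not the same as reviewing answers.
2. **Pause and counselling.** These are conditional on apparent distress. An answer on the screen is not a condition.
3. **Advice and referral.** These are wider, since they include participants in need. The text does not say how need is recognised, and does not mention questionnaire answers.
4. **Traceability.** The Data Storage and Protection section puts participant numbers on the computer-interview logs, and "an identifier key will be created to link the PIN to participant names and contact information". The answer can be traced to a person afterwards, but no time for reading it is given. The 48-hour review in that section covers qualitative recordings only, and the daily monitoring described under Measures covers game activity.
5. **Other safeguards.**
   - Iterative open trial, Procedures: one brief adherence counselling session after consent and assessment, and counsellor contact as needed. The pilot uses the same procedures, subject to open-trial feedback, and controls receive the same standard of care. The session concerns adherence and is not stated to recur at 6 and 12 months.
   - Inclusion criteria: a resource packet for everyone.
   - Medical or Professional Intervention: physician care, and adverse events reported at once to the PI. An item 17 endorsement is not defined as an adverse event.
   - Protection Against Risk, item 3: consent will cover legal duties to break confidentiality.
   - Interview and focus-group guides: an exception to confidentiality for danger, covering what participants tell staff.

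   None of these visibly acts on the item 17 answer before the participant leaves.

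**Number of administrations**, to size the fix only. The plan gives no figure, and its assessment schedule (Figure 5) is not shown.

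- Pilot baseline only: 60.
- Every pilot assessment without loss, plus ten open-trial participants assessed twice: 60 × 3 + 10 × 2 = 200.
- With the plan's 52 retained at 12 months and between 52 and 60 present at 6 months: 60 + 52 + 52 + 20 = 184, up to 60 + 60 + 52 + 20 = 192.

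The documents give no endorsement rate. If 2% to 20% is assumed, the number of alerts runs from 60 × 0.02 = 1.2 to 200 × 0.20 = 40 over the whole study. That range sizes workload; it does not estimate missed participants.

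**The case against.** The strongest reply is that the natural homes for a suicide-risk procedure are the Data and Safety Monitoring Plan, the consent form and the standard operating protocol, and none could be read. This stands as a limit. A reader might infer that the trial has no procedure for suicidal thoughts; the documents do not support that, because only the visible trigger can be judged.

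The second reply is that participants are not left to fend for themselves. This also stands in part. A reader might infer that outside help reaches a calm participant only on request or in print. That goes too far: a counselling session is scheduled after the enrolment assessment, and every participant is under a physician's care. But nothing visible tells the counsellor or physician what was answered. Need-based advice and referral are likewise real safeguards, but without a visible step that finds need from the answers.

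A reader might also infer that participants are promised that nobody will see their item 17 answer. The privacy statement in Appendix 3 introduces the Adolescent Risk Behavior Assessment and describes that section's content, so it does not clearly reach item 17.

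Finally, no estimate, test or power figure depends on this, and the schedule is unseen, so the visits at which the item is asked cannot be confirmed. Both points are correct and keep the matter in proportion.

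**Conclusion.** The concern holds for the visible trigger. Pause and counselling begin from apparent distress, advice and referral depend on a need that no visible sentence ties to an answer, and the item is self-entered. A participant who endorses item 17 calmly and says nothing could leave without that answer being seen.

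This is an inexpensive safety improvement, not a flaw in the analysis: no trial estimate changes. How many participants would be affected cannot be said, since no endorsement rate is given. The conclusion assumes that the unseen texts do not already provide a same-visit check. If they do, only a cross-reference is missing.

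**What to change.** First check the Data and Safety Monitoring Plan, consent form and standard operating protocol. If any of them already covers endorsement of item 17, cross-refer to it under Emotional discomfort and stop there. Otherwise add a second trigger to that section:

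1. A score of 1 or more on item 17, or another threshold that the investigator fixes in advance, produces an alert when the computer interview is completed. If the software cannot do this, staff check that one answer at each administration before the participant leaves.
2. An on-site clinic counsellor or physician speaks with the participant the same day. The Co-PI psychologist's advice and the referral then follow as already described.
3. Before the scale, participants are told that staff may see answers indicating danger. The existing consent provision on breaking confidentiality can be extended for this, with the danger exception in the interview guides as model wording.

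As an optional edit, limit the privacy statement in the Adolescent Risk Behavior Assessment introduction to its own section.

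Costs: a short staff briefing, the same-day conversations, and, if no alert is possible, a check at each of about 60 to 200 administrations. Whether the software supports an alert is not documented. Telling participants that staff may see the answer could lower endorsement somewhat, by an unknown amount.

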Measures: Participants' overall satisfaction with the game will be assessed using a modified version of the Client Satisfaction Questionnaire (CSQ-8) after each iteration. The CSQ is an 8-item measure with good reliability and validity and used previously with African samples (46). They will also complete a modified Session Evaluation Form (SEF), which has 13 items that reflect areas of feasibility and intervention utility. Participants will complete measures of main study outcomes using an audio-assisted computer self-interview (ACASI). Main outcome measures are listed in the next section. The last prototype will be reviewed and revised by the research team before being finalized. **Training of Research Assistants (RAs), Fidelity Monitoring, and Supervision:** RAs will be trained by the co-PI ([name]) over a period of two days to provide

game instructions. Game instructions will be audio-recorded and coded for fidelity. Problems with fidelity will trigger retraining of RAs by the PI. Peer educators will receive in-person supervision from study staff who will themselves receive Skype supervision from the [name]. [name] will also monitor participants' game activity daily via the system's website.

Randomized Controlled Pilot Phase (Aim 2)

We will evaluate the preliminary impact of the Text-Based Adherence Game run for one year compared to a control group. The pilot will include 60 YPLH on ART with the same eligibility criteria as the open trial. The same procedures will also be used pending open trial feedback. The game will be evaluated via a baseline and two follow-up assessments (6-/12-months post-baseline). Randomization will occur after enrollment using a random number generator. Participants not randomized to the Text-Based Adherence Game will receive the SOC condition as described above. See Figure 4.

Figure 4. Steps for Aim 2 Randomized Controlled Pilot

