Hypothesis One (Aim 1). The Text-Based Adherence Game will be feasible, appealing, and useful. YPLH in the third open trial iteration of the Text-Based Adherence Game will show shifts in primary and secondary outcomes in the expected directions from pre-post assessments.

Hypothesis Two (Aim 2). Compared to participants in the control group, participants in the Text-Based Adherence Game will show at 6 and 12 months post-intervention: improved ART adherence, clinic attendance, biologic functioning (lower

Figure 5. Assessment Schedule

HIV viral load, higher CD4 count), and shifts in secondary outcomes (social support, self-efficacy, etc.) consistent with adherence promotion. Repeated measures ANCOVAs will be used to test differences over time between study conditions on each outcome variable. Missing data will be handled using multiple imputation. Potential imbalance between treatment conditions on baseline characteristics will be addressed using inverse probability of treatment weights (51). Power: As this is a pilot study and the impact of the intervention is not known, there may not be adequate power to determine its efficacy; also, pilot studies are not designed to provide accurate estimates of effect sizes upon which to base large trials(52). However, the small pilot may provide a “signal” of impact on its primary outcomes and we will examine the effects of the intervention on secondary outcomes based on Social Action Theory. We assume that retention over one year is at least 86% based on past studies conducted in Ghana (31, 53) thus 52 cases of the 60 enrolled in the pilot are available for analysis. Power analyses were run with G*Power 3(54). The model assumed 3 assessments with 52 individuals. The analyses with alpha of 0.05 and power 0.80 will be able to detect small to medium effects.

DISSEMINATION OF RESULTS

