Do you pay for a plan to make phone calls or send text messages? 1- Yes 2- No

How often do you play videogames on a console (computer, Xbox, Playstation)?

1- Every day	4- Once or twice a month
2- Three to four times a week	5- Less than once per month
3- Once or twice a week	

How often do you play games on your phone?

1- Every day	4- Once or twice a month
2- Three to four times a week	5- Less than once per month
3- Once or twice a week	

Do you own a computer or laptop at home? 1- Yes 2- No

How easy or hard is it for you to access a laptop or computer?

1- Very easy	3- Hard
2- Easy	4- Very Hard

How easy or hard is it for you to access the internet on your phones?

1- Very easy	3- Hard
2- Easy	4- Very Hard

How easy or hard is it for you to access the internet on a computer?

1- Very easy
2- Easy
3- Hard
4- Very Hard

How easy or hard is it for you to access wifi on your computer or phone?

1- Very easy
2- Easy
3- Hard
4- Very Hard

Can you access the internet daily or almost daily? 1- Yes 2- No

SATISFACTION SURVEYS

Client Satisfaction Questionnaire

Please help us improve our program by answering some questions about the Intervention. We are interested in your honest opinions, whether they are positive or negative. *Please answer all of the questions.* We also welcome your comments and suggestions. Thank you very much; we really appreciate your help.

Circle your answer:

1. How would you rate the quality of the game you played? Excellent, Good, Fair, or Poor.
2. Did you get information you wanted? No, definitely. No, not really. Yes, generally. Yes, definitely.
3. Would this game meet your needs?
 - Almost all of my needs would be met
 - Most of my needs would be met
 - Only a few of my needs would be met
 - None of my needs would be met
4. If a friend were interested in a similar game, would you recommend this one? No definitely not. No, I don't think so. Yes, I think so. Yes definitely.
5. How satisfied are you with the amount of activities involved with the game?
Quite satisfied, Indifferent or mildly dissatisfied, mostly satisfied, very satisfied.
6. Did the game help you to deal more effectively with issues important to you? Yes, it helped a great deal. Yes, it helped. No, it really didn't help. No, it seemed to make things worse.
7. In an overall, general sense, how satisfied are you with the game. Very satisfied. Mostly satisfied. Indifferent or mildly dissatisfied. Quite dissatisfied.

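### Client Satisfaction Questionnaire item 5 offers *Quite satisfied* where item 7 has *Quite dissatisfied*, so its options are out of order and none records clear dissatisfaction

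*Combined protocol and SAP*

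**What the plan says.** The Measures paragraph for the iterative open trial says that participants' "overall satisfaction with the game will be assessed using a modified version of the Client Satisfaction Questionnaire (CSQ-8) after each iteration". It adds: "The CSQ is an 8-item measure with good reliability and validity". The scale informs Hypothesis One in the Data Analytic Plan: "The Text-Based Adherence Game will be feasible, appealing, and useful".

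The form is in Appendix 3, under Satisfaction Surveys. Item 5 asks "How satisfied are you with the amount of activities involved with the game" and offers "Quite satisfied, Indifferent or mildly dissatisfied, mostly satisfied, very satisfied". Item 7, on overall satisfaction, offers "Very satisfied. Mostly satisfied. Indifferent or mildly dissatisfied. Quite dissatisfied".

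The form invites negative as well as positive opinions and asks for an answer to every item. The options are words to be circled. No numeric codes, item directions, total score or cut-off appear on the form or in the Data Analytic Plan.

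**The concern.** Item 5 has three satisfied answers, one indifferent or mildly dissatisfied answer, and nothing stronger on the negative side. Its first option is a satisfied one, in the slot where the pattern of the form calls for the most negative answer.

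This is a form that will be administered, and the open trial section says that what is learned after each iteration is used to change the game. Item 5 is also the only rated question on the amount of activities. The nearest rated item on the Session Evaluation Form asks only whether participants could do the activities. A participant who found the amount clearly wrong could not say so on this item, and a satisfied participant might be coded as the opposite.

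**Working it through.** The plan states no figure for this scale, so there is none to reproduce. The check is a comparison of wording, followed by an illustration of the scoring effect.

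**1. Items 5 and 7 side by side, item 7 read from last option to first**

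| Slot | Item 7, reversed | Item 5, as printed |
|---|---|---|
| 1 | Quite dissatisfied | Quite satisfied |
| 2 | Indifferent or mildly dissatisfied | Indifferent or mildly dissatisfied |
| 3 | Mostly satisfied | Mostly satisfied |
| 4 | Very satisfied | Very satisfied |

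Three of the four slots agree. Changing one word in slot 1 makes item 5 the exact mirror of item 7.

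**2. Which end of item 5 is the negative end**

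Item 2 runs from negative to positive: "No, definitely. No, not really. Yes, generally. Yes, definitely". Items 4 and 8 do the same, and slots 2 to 4 of item 5 rise in the same direction. Items 1, 3, 6 and 7 run the other way. So slot 1 of item 5 is where the most negative answer belongs.

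**3. If items are scored by position**

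Assumption, not in the documents: each item scores 1 to 4, with 1 at its negative end. The eight-item total then runs from 8 to 32, a range of 24.

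- A satisfied participant who picks *Quite satisfied* scores 1. *Mostly satisfied* would give 3 and *Very satisfied* 4. The loss is 3 − 1 = 2 to 4 − 1 = 3 points, or 2/24 = 8.3% to 3/24 = 12.5% of the range.
- A clearly dissatisfied participant whose nearest answer is slot 2 scores 2 where a complete scale would give 1: 2 − 1 = 1 point too high.

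The open trial plans iterations of 6, 8 and 10 participants. The effect of one affected participant on the iteration's mean total is the points divided by n:

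| n | One satisfied participant in slot 1 (too low by) | One clearly dissatisfied participant in slot 2 (too high by) |
|---|---|---|
| 6 | 2/6 to 3/6 = 0.33 to 0.50 | 1/6 = 0.17 |
| 8 | 2/8 to 3/8 = 0.25 to 0.38 | 1/8 = 0.13 |
| 10 | 2/10 to 3/10 = 0.20 to 0.30 | 1/10 = 0.10 |

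**4. If items are scored by meaning**

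A scorer who treats *Quite satisfied* as a satisfied answer avoids the loss in step 3. Two faults remain. The lowest available answer is still indifference or mild dissatisfaction. And nothing says whether *quite* ranks below, level with or above *mostly* satisfied, so the codes for the satisfied options are arbitrary.

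The item is therefore faulty under either rule. Only the point loss in step 3 depends on scoring by position.

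**The case against.** **The change may be deliberate.** The protocol calls the questionnaire a modified version. But a considered modification would hardly put *Quite satisfied* next to *Indifferent or mildly dissatisfied* and leave item 7 unlike item 5. This does not stand.

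**The text may have been misread from the PDF.** That cannot be fully excluded. However, *dissatisfied* is read correctly later in the same line and twice in item 7. It is a reason to check the deployed form first.

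**No scoring rule is given, so no scoring error can be asserted.** This stands. A reader might infer that the satisfaction total will be wrong in both directions. The documents do not support that: they give no key, and because half the items run each way, any scorer must set direction item by item and could code this option by its meaning. For the same reason a sized shift in the group mean cannot be claimed. It would need the share of participants choosing the first option, for which the documents give no figure.

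**The scale carries little weight.** This largely stands. A reader might take the questionnaire as a main measure for Hypothesis One. The open trial section keeps its main outcome measures for a separate list of adherence, clinic visits, viral load and CD4 count. Acceptability is also assessed with the 13-item Session Evaluation Form and a cognitive interview after each iteration. The interview guide asks what participants would change and what they thought of the message frequency, so dissatisfaction has another route into the record. Hypothesis One sets no threshold on the questionnaire.

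**Staff are on hand.** Appendix 3 says that items are read out by a computer program and staff are available to help. That may reduce confusion, but it does not supply the missing answer.

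**Conclusion.** The point holds as a drafting error in an instrument that will be used. Item 5 is unordered and cannot register clear dissatisfaction with the amount of activities; both follow from the printed text alone. A loss of 2 to 3 points for a satisfied participant who picks the first option, and a gain of 1 point for a clearly dissatisfied one, rest on assumed 1-to-4 scoring by position.

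The consequence is small: one item of eight, in one of several acceptability measures, with no stated decision resting on the total. Adherence, clinic attendance, viral load, CD4 count and the sample size are unaffected. It merits correction because iteration feedback shapes the game and, in groups of 6 to 10, a single miscoded answer is visible in the mean.

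**What to change.** 1. Check the form as deployed, on paper or in the computer program, against Appendix 3.
2. Change the first option of item 5 to *Quite dissatisfied*.
3. Add a short scoring key that gives the codes and direction of each item: items 1, 3, 6 and 7 run from positive to negative, and items 2, 4, 5 and 8 from negative to positive.
4. If any iteration has already used the printed wording, leave item 5 out of the total for all iterations, so that every total rests on the same items. Record which wording each iteration used.

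Before first use, the cost is one word and a few lines of key. If the printed wording has been used, the cost is a seven-item total (7 to 28 under the assumed coding) and no comparable rating of the amount of activities across iterations.
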